11.1 Minimal risks and constraints added by the research

The risks and constraints for the patient will only be the extra time spent by the patient on the ultrasound. Ultrasound is a non-invasive, non-irradiating and totally painless tool.

11.2 Expected benefits for the patient

Ultrasound allows a quantitative and qualitative evaluation of the structures involved in swallowing disorders. It is a non-invasive, non-irradiating diagnostic tool that can be performed in a consultation. To our knowledge, there is no ultrasound score for the diagnosis of swallowing disorders. Videofluoroscopy is an irradiating examination, requiring the displacement of the patient and mobilizing a specialized multidisciplinary team. We expect excellent reliability and validity of ultrasound in the diagnosis of swallowing disorders, which

would make it possible to propose an alternative examination to videofluoroscopy that would be more easily performed on an outpatient basis, non-invasive and non-irradiating.

12 Feasibility

The Forcilles Hospital has a technical platform dedicated to the HDJ deglutition with a capacity of three patients per week, at a rate of one patient per day for three days. Given the difficulty of the surrounding health structures to have the human and technical resources to carry out the examinations proposed in this HDJ deglutition, many patients are referred to the Forcilles Hospital. The data relating to admissions over the last two years allow us to envisage 90 patients over a 10-month period.

The medical and physiotherapy team has experience in clinical research, as they are already involved in other ongoing research projects (<https://clinicaltrials.gov/ct2/show/NCT02881814>, <https://clinicaltrials.gov/ct2/show/NCT02474797> and <https://clinicaltrials.gov/ct2/show/NCT04373811>).

Taking into account the inclusion and non-inclusion criteria, possible refusals of patients to participate in the research, potential exclusions and the recruitment experience, we estimate a minimum recruitment capacity of 50% of patients with risk factors for swallowing disorders admitted to HDJ for evaluation of these disorders, i.e. 100 patients in 25 months

13 Ethical and regulatory aspects

The Forcilles-Fondation Cognacq-Jay hospital promoter and the person(s) directing and supervising the research undertake to ensure that this research is carried out in accordance with law n°2004-806 of 9 August 2004 relating to public health policy and the regulatory provisions in force (articles L.1121-1, L.1121-2 and L.1121-3 of the Public Health Code. The data recorded during this research will be subject to computerised processing in compliance with law n°78-17 of 6 January 1978 relating to information technology, files and freedoms, amended by law n° 2018-493 of 20 June 2018 (decree n° 2018-687 of 1° August 2018) and order n° 2018-1125 of 12 December 2018.

The research will be conducted in accordance with this protocol.

13.1 Role of the promoter

The research commission of the Forcilles-Fondation Cognacq-Jay hospital, promoter of this research, submits the file to the opinion of the relevant Comité de Protection des Personnes

(CPP) (CPP Ouest III) whose opinion will be notified in the information note intended for the persons concerned.

The natural or legal person who initiates the research, manages it and ensures that it is financed is called the sponsor.

13.2 Submission to the PPC

This research will be submitted to a Committee for the Protection of Individuals, which will be drawn by lot within the framework of the "Jardé law" (article L.1121-4 of the Public Health Code, decree no. 2016-1537 of 16 November 2016, which came into force on 18 November 2016).

The opinion of the above-mentioned committee is notified in the information note intended for the persons concerned. A copy of this opinion and a summary of the research will be sent to the ANSM.

13.3 Data protection

This research is subject to law n°78-17 of 6 January 1978 relating to information technology, files and freedoms as amended by law n° 2018-493 of 20 June 2018 (decree n° 2018-687 of 1 August 2018). Information on the rights of persons participating in this research (right of access and rectification, right to object to the transmission of data covered by professional secrecy likely to be used in the context of this research) is included in the information note intended for the patient.

A reference methodology specific to the processing of personal data carried out in the context of biomedical research defined by Law 2004-806 of 9 August 2004 as falling within the scope of Articles L.1121-1 et seq. of the Public Health Code was updated by the CNIL in May 2018 (Deliberation No. 2018-153 of 3 May 2018) following the publication of European Regulation No. 2016/679 (General Data Protection Regulation). This methodology allows a simplified declaration procedure when the nature of the data collected in the research is compatible with the list provided by the CNIL in its reference document. This study is part of the MR001 reference methodology to which the Forcilles-Fondation Cognacq-Jay hospital has committed to comply.

13.4 Insurance

The Sponsor takes out insurance covering its own civil liability and that of any person involved in the performance of the research for the entire duration of the research, regardless of the nature of the links between the participants and the Sponsor (Article L.1121-10 of the Public

Health Code). The sponsor is also responsible for the compensation of the harmful consequences of the research for the person who undergoes it and for that of his or her dependents, unless it can be proved that the damage is not attributable to its fault or to that of any other party involved, without the possibility of invoking the act of a third party or the voluntary withdrawal of the person who initially agreed to undergo the research. Where the sponsor is not liable, the victims may be compensated under the conditions set out in Article L.1142-3.

The Forcilles-Fondation Cognacq-Jay hospital has taken out insurance under contract no. 163607 guaranteeing its civil liability as well as that of any intervening party with the company SHAM for the entire duration of the research, in accordance with article L.1121-10 of the Public Health Code.

13.5 Substantial amendment to the protocol

The investigator or coordinator informs the research commission of the Forcilles-Fondation Cognacq-Jay hospital of any proposed modification of the protocol. Any substantial modification will be submitted by the sponsor of this research to the CPP for its opinion.

13.6 Information note and express consent

In accordance with Article L.1122-1 of the Public Health Code, the information provided to the persons who are to be involved in the research is the subject of a written document submitted in advance to the personal protection committee. The ethical opinion of the CPP Ouest III has been requested.

The investigator at the centre offers the patient, or a relative if the patient is incapacitated, to participate in the study. The investigator informs the patient orally of the terms of the study and gives him/her the information note. If the patient gives free, informed and express oral consent to participate in the protocol, the information given orally and in writing, as well as the collection of oral consent, will be recorded in the patient's medical record.

In the event that a relative of the patient has given consent, as soon as possible, the patient will be informed of the research and asked for oral consent for the possible continuation of the research.

Patients are free to participate or withdraw from the study at any time in accordance with Article 21 of the GDPR. Data collected until the patient withdraws consent will be used unless the patient expressly requests otherwise. The withdrawal of consent by the patient and the agreement to use or not the data previously collected will be traced in the patient's medical file.

When the research is completed, the person who is to be the subject of the research may be informed of the overall results of the research in a manner to be specified in the information document.

13.7 Expected deadline for publication of results in an international journal

The deadline for the publication of the results is 30 months.

13.8 Data management

For each subject, an identification code (corresponding to the centre number-inclusion number-Initial Surname-Initial First Name) will be assigned. The data collected will be confidential and coded (only the identification code will appear). The concordance table linking the assigned identification code and the participant's name will be kept by the principal investigator in a file with computer restricted access rights. The data will be entered into a password protected Excel® file held by the principal investigator. Data processing and statistical analysis will be carried out at the Forcilles-Fondation Cognacq-Jay hospital.

The promoter is the owner of the data and no use or transmission to a third party can be made without his prior agreement.

The specific documents of a type 2 interventional research ("Loi Jardé", decree n° 2016-1537 of 16 November 2016, which came into force on 18 November 2016) with minimal risks and constraints will be archived by all parties for a period of 15 years after the end of the research.

This indexed archive includes :

- successive versions of the protocol (identified by version number and date);
- correspondence ;
- the inclusion list or register ;
- the data collection document ;
- research-specific annexes ;
- the final report of the research.

The database used for the statistical analysis must also be archived by the person responsible for the analysis (paper or computer).

13.9 Human and financial resources

The Forcilles-Fondation Cognacq-Jay hospital is equipped with human, material and technical resources to carry out this research project.

15 ANNEXES

15.1 Appendix 1: Dysphagia Outcome and Severity Scale

Completely oral feeding: normal diet

- Level 7: Normal in all situations
- Level 6: Functional swallowing; with functional limitations/independent with modifications

Modified scheme and/or adaptations

- Level 5: Mild dysphagia; mild monitoring, may require restriction of one type of texture
- Level 4: Mild to moderate dysphagia: intermittent monitoring, one or two restricted textures
- Level 3: Moderate dysphagia: full assistance, supervision, two or more restricted textures

Need for additional artificial nutrition

- Level 2: Moderate to severe dysphagia: significant assistance or need for strategies with partial oral feeding (tolerates at least one texture with use of strategies)
- Level 1: Severe dysphagia: no oral feeding: unable to tolerate oral intake

15.2 Appendix 2: Penetration-aspiration scale

Category	Score	Description
No penetration or suction	1	The material does not fit into the VA
Penetration	2	The material enters the VA, remains above the vocal cords and is ejected from the VA
	3	The material enters the VA, remains above the vocal cords and is not ejected from the VA
	4	Material contacts the vocal cords and is ejected from the VA
	5	Material contacts the vocal cords and is not ejected from the VA
Suction	6	Material enters the VA, passes through the vocal cords and is ejected into the larynx or out of the VA
	7	The material enters the VA, passes through the vocal cords, and is not ejected from the trachea despite patient effort
	8	The material enters the VA, passes through the vocal cords and no ejection effort is made by the patient

15.3 Appendix 3: Procedure for performing Videofluoroscopy

- **Conduct of the examination :**

The examination must be carried out in the presence of the radiologist and the doctor and speech therapist responsible for the HDJ care.

All professionals will ensure that they have the necessary equipment to monitor the patient's vital parameters. If alterations in vital parameters, patient discomfort or any other reason for stopping the examination, the doctor will fill in the adverse event sheet.

If the examination could not be finalised, the patient will be excluded from the protocol. The exclusion of the patient for non-interpretable examination will be noted in the research observation booklet.

Swallowing trials will be conducted in the quantities and textures described above. The food will be mixed with barium to allow for vision.

For each trial, we will ask the patient to take the food/liquid and swallow it after the professional has indicated.

Tests 1-4 will be performed in lateral projection. Test 5 will be performed in anteroposterior projection.

- **Patient position:**

- Lateral projection (trials 1-4) :

[figure not shown]
The patient is seated and the image is oriented to find a vertical alignment of the C2-C4 vertebrae. The anterior-inferior border of C4 and the body of the hyoid bone will be used as a reference for the evaluation of laryngeal movement. (74)(75).

- Anteroposterior projection (try 5) :

Again the patient will be seated, perpendicular to the rays, in a comfortable position.

Swallowing tests of fine liquid in a glass will be performed to observe unilateral abnormalities (asymmetry, paralysis or paresis).

Figure1. Example of projections and patient set-up. Taken from : "La réhabilitation de la déglutition chez l'adulte" Woissar-Bassols V.

- **Sequence of testing :**

Chronology of the tests	Product and quantity	Signs of disorder (yes/no)	Specify the structure(s)/function(s) in deficit	Pathophysiological mechanism	PAS score
1	5ml of the fine liquid				
2	5ml of the thick liquid				
3	Drink 30ml from a glass				
4	Chew and swallow 1 teaspoon of solid food				
5	Drinks 30ml of the thin liquid from a glass				

Record, for each food trial :

- The onset of swallowing disorder signs
- The structure(s) suspected of causing the disorder. If the cause of the disorder has not been identified, the SLT will indicate "NI".
- The pathophysiological mechanism identified, according to the table above
- The score corresponding to the PAS scale

Reminder of the physiopathological mechanisms that can be demonstrated:

[figure not shown]
N°	Pathophysiological mechanism	N°	Pathophysiological mechanism
1	Anterior closure defect of the oral cavity	7	Failure to initiate pharyngeal time
2	Posterior closure defect of the oral cavity	8	Lingual propulsion defect
3	Velopharyngeal closure defect	9	Pharyngeal propulsion defect
4	Failure to initiate oral time	10	Failure of the tongue base to recede
5	Defects in the control of the food bowl	11	Laryngeal ascension defect
6	Failure to transport orally	12	Failure to open the SSO

Reminder of the foods that can be used for each texture: *Palmer et al. Dysphagia (1993)*

[figure not shown]
Category	Examples
Fine liquid	Fruit juice, soda, water
Thick liquid	Gazpacho milshake
Ultra thick liquid	Yoghurt, pudding
Mouldable solid (type A)	Mashed potatoes, soft cookies
Special solid (type B)	Hamburguer
Multitexture (type C)	Spaghetti with meat, beef steak

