1.3.2 Radiology and fibroscopy

The literature agrees that videofluoroscopy (VFSS) and swallowing fibroscopy are the gold standards for swallowing assessment. (26)(27) Different quantities and textures, which will evolve progressively according to the outcome of the first feeding trials, will be used to assess the patient's swallowing abilities.

Real-time visualization of swallowing will allow the clinician to objectify inhalation as a sign of a swallowing disorder (28) and to estimate its severity by means of scores such as the "Dysphagia outcome and severity scale" (DOSS) or the "Penetration-Aspiration Scale" (PAS). (29)(30)(31) (**Appendices 1 and 2**).

For VFSS, the liquids/foods administered to the patient are mixed with barium in order to follow the course of the food bolus. This allows the assessment of all three phases of swallowing and a better assessment of the oral phase compared to nasofibroscopy of swallowing (FEES). However, it does not allow the analysis of the anatomy of structures and requires the patient to be transported to an equipped room and exposed to radiation.

The FEES, thanks to its location at the tip of the epiglottis during the examination, has the advantage of allowing the evaluation of tissues, possible local trauma or the presence of secretions. In addition, it allows the evaluation of the sensitivity of the larynx. However, this examination is often uncomfortable for the patient and requires the frequent use of a local anaesthetic which alters sensitivity. (6) Physiological movements during swallowing make it

difficult to see the vocal cords. The examiner will have to lower the fiberscope afterwards to look for signs of inhalation. Furthermore, there is a lack of a standardised protocol. (32)

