7.1 Operator training in ultrasound

The ultrasound examination will be performed by a physiotherapist, blind to the totality of the examinations performed on the patient. The details of the ultrasound examination carried out within the framework of the protocol can be found in **appendix 4**.

The operator training is as follows:

- 3 days of theoretical and practical training;
- More than 100 ultrasounds supervised by a radiologist;
- Two years of independent practice.

Similarly, all the physiotherapists performing the ultrasound scans are already involved in other research projects using lung, diaphragm and peripheral muscle ultrasound:

<https://clinicaltrials.gov/ct2/show/NCT02474797>,

<https://clinicaltrials.gov/ct2/show/NCT02881814>

and

<https://clinicaltrials.gov/ct2/show/NCT04373811>

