8.3 Visit of the ultrasound operator

The ultrasound examination is the first examination performed in order to maintain the operator's ultrasound blindness. It will take place in the consultation room provided in the HDJ.

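### Appendix 3 excludes every unfinished videofluoroscopy on a ground that fits only non-interpretable ones, and no safeguard keeps ultrasound findings from those completing the reference record

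*Combined protocol and SAP*

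**What the plan says.** All places are in the combined protocol and SAP.

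**Exclusion.** Appendix 3 (15.3) states: "If the examination could not be finalised, the patient will be excluded from the protocol". It continues: "The exclusion of the patient for non-interpretable examination will be noted in the research observation booklet". The reasons for stopping are open-ended: "If alterations in vital parameters, patient discomfort or any other reason for stopping the examination, the doctor will fill in the adverse event sheet". No section defines a finalised or an interpretable examination, and section 9 does not mention incomplete VFSS.

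**The VFSS record.** The Appendix 3 form has one row for each of five swallows, with a yes/no entry for signs of disorder, the structure at fault, the mechanism, and "The score corresponding to the PAS scale". The speech therapist makes entries in it: "If the cause of the disorder has not been identified, the SLT will indicate" a code for not identified.

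**Use of the result.** The VFSS diagnosis is the outcome for the thresholds (9.4). It forms the positive and negative groups (9.5), is predicted by the model that gives the weights (9.6), and is the reference for accuracy (9.7.2). Section 9.5 does not say how five swallow records become one positive or negative diagnosis.

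**Masking.** Section 7.1 states: "The ultrasound examination will be performed by a physiotherapist, blind to the totality of the examinations performed on the patient". Section 8.3 adds: "The ultrasound examination is the first examination performed in order to maintain the operator's ultrasound blindness". No section masks the radiologist, the doctor or the speech therapist to the ultrasound.

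**The concern.** The two sentences of Appendix 3 describe different sets of patients. An examination stopped after the second swallow is unfinished, but a clear positive on the first swallow is still interpretable. Read literally, that patient leaves the study and the positive reference result is lost. Read by the stated ground, the patient stays. Two members of staff could classify the same patient differently.

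Exclusion might also depend on the reference result, since altered vital parameters are a named reason for stopping. If so, patients are dropped according to the outcome being predicted. The case mix and prevalence behind the variable selection, weights, thresholds and predictive values would then change.

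The masking question is separate. The ultrasound comes first and VFSS last. Under 8.5 the speech therapist, after VFSS, summarises the day using the results of its various investigations, and ultrasound is not excepted. Under 8.6 results are transcribed into the research book at the end-of-day visit. If ultrasound findings were known when the VFSS record was completed, agreement between the two tests could be inflated.

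**Working it through.** **Plan's own figure (9.1).** Five variables, 10 events per variable, 50% prevalence: 5 × 10 / 0.50 = 100 patients, which reproduces. The plan therefore expects 50 positives and 50 negatives.

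**Assumptions.** The documents give no stop rate. I let a share f of all 100 examinations be stopped, with f from 5% to 20%.

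**Analysed prevalence under the current rule (all stopped examinations excluded).**
- All stopped are positive, (50 − 100f) / (100 − 100f): 45/95 = 47.4% at 5%; 40/90 = 44.4% at 10%; 30/80 = 37.5% at 20%.
- Both groups stop equally: for example 40/80 = 50% at 20%.
- All stopped are negative, 50 / (100 − 100f): 50/95 = 52.6%; 50/90 = 55.6%; 50/80 = 62.5%.

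**Events per variable if all stopped are positive.** Section 12 already allows for potential exclusions in its recruitment estimate of 100, so I hold the number analysed at 100. Then 47.4/5 = 9.5, 44.4/5 = 8.9 and 37.5/5 = 7.5, against 10 planned. If instead 100 are enrolled and excluded patients are not replaced, f of 5% and 20% give 45/5 = 9.0 and 30/5 = 6.0.

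**Direction of bias in sensitivity.** Assume ultrasound detects 75% of completed positives and that all stopped examinations are positive. The reported figure is then 75%.
- If it would detect 95% of stopped positives, sensitivity in all 50 is (5 × 0.95 + 45 × 0.75)/50 = 77% with 5 stopped, and (20 × 0.95 + 30 × 0.75)/50 = 83% with 20. The report is 2 to 8 points too low.
- If it would detect 55% of them, sensitivity is 73% and 67%. The report is 2 to 8 points too high.
- If detection is the same in both, there is no bias in sensitivity.

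**Whether another handling cures this.** Take 20 of 100 stopped, and assume that a truly negative patient never has a recorded positive swallow. The truth is 50% in every row. The proposed main analysis keeps every examination with an interpretable swallow and classifies it by one rule. The last two columns count all stopped examinations without a recorded positive swallow as positive, then as negative.

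| Stopped examinations | Current rule | Proposed main | Counted positive | Counted negative |
|---|---|---|---|---|
| 20 positive, all with a positive swallow | 30/80 = 37.5% | 50% | 50% | 50% |
| 20 positive, 10 with a positive swallow, 10 with only negative swallows | 37.5% | 40/100 = 40% | 50% | 40% |
| 10 positive (all with a positive swallow), 10 negative and interpretable | 40/80 = 50% | 50% | 60/100 = 60% | 50% |
| 20 negative, interpretable | 50/80 = 62.5% | 50% | 70/100 = 70% | 50% |
| 20 negative, none interpretable | 62.5% | 62.5% | 70% | 50% |

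No column returns 50% in every row.

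**Masking.** Sections 7.1 and 8.3 protect the ultrasound operator only. Sections 8.5 and 8.6 and Appendix 3 neither describe a release of ultrasound findings to those completing the VFSS record nor prevent one. This cannot be sized.

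**The case against.** **One ground may be intended.** Appendix 3 sets a five-test sequence, the last in a different projection. Requiring all of it is a defensible design choice, and in a translated text the two sentences may simply treat an unfinished examination as non-interpretable. That is a possible reading. It does not remove the loss of positives already recorded, or the chance that the loss depends on the outcome.

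**The link to outcome is unproved.** Discomfort and any other reason stand beside altered vital parameters. Section 1.3.2 says of the quantities and textures, "which will evolve progressively according to the outcome of the first feeding trials", but that is background and cuts both ways, since a shortened sequence might still count as finalised. This stands. A reader might infer that the rule removes the most severe patients, or that it overstates accuracy. The documents support neither.

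**The effect may be small.** The illustrated shift of 2 to 8 points is below the 95% interval half-width of 1.96 × √(0.75 × 0.25/50) = 12 points. That is true, but the interval does not cover selection.

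**Masking is the weaker part.** A reader might infer that the VFSS readers are unblinded. The documents do not say so. Section 8.7 places the PAS and Dysphagia Outcome and Severity Scale entries at the imaging step. The consultation meeting in 6.1 does not list the ultrasound operator. The score weights and most thresholds are set only after data collection, so no score result exists that day. Raw measurements and qualitative signs do exist, however, and nothing keeps them from those completing the VFSS record.

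**Conclusion.** The point holds as a mismatch in the text with a plausible route to bias. The exclusion trigger is wider than its stated ground, and the literal rule can discard an interpretable positive reference result. If stopping is linked to the VFSS result, this reaches the selection of variables (the primary outcome) as well as the weights, thresholds and accuracy estimates. Neither that link nor the direction of bias is established.

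The prevalence range of 37.5% to 62.5% and the 7.5 events per variable are extremes that assume 20% of all examinations stop and all the stopped belong to one group. With equal stopping, prevalence does not move. At a 5% stop rate the range is 47.4% to 52.6%.

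The masking gap is real as an absent safeguard and goes no further than that. Both parts should be corrected, because the changes are cheap and are best made before results are seen.

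**What to change.** Leave the decision on when to stop an examination to the clinicians. Then:

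1. Reconcile the two sentences of Appendix 3 so that only examinations with no interpretable swallow are excluded, and keep the per-swallow data of every stopped examination.
2. State in 9.5 the rule that turns the per-swallow record into a positive or negative VFSS, and apply it to completed and stopped examinations alike. The steps below depend on this rule. Use the resulting single set as the main analysis, both to derive the score and to estimate its accuracy.
3. As sensitivity analyses, repeat with all stopped examinations excluded (the current rule), then with stopped examinations without a recorded positive swallow counted all positive, then all negative.
4. Report the number of stopped examinations and the reasons, and state that no handling is shown to be unbiased.
5. Require that the Appendix 3 VFSS record be completed before any ultrasound finding is available to those who complete it.

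The cost is mainly wording. The per-swallow form, the adverse event sheet and the booklet entry for exclusions already exist. The downsides are that some reference results will rest on fewer than five swallows, there is a little more analysis work, and the release of ultrasound findings is briefly delayed.

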7.2 Practical details of the ultrasound examination

The examination, the details of which can be found in **Appendix 4**, is carried out using a Sonoscape Expert 2 ultrasound scanner (Digital Color Doppler Ultrasound System; Sonoscape medical corp. China) equipped with a linear probe (7-10 MHZ) and a convex probe (3-5 MHZ). Both probes will be used for each of the swallowing trials.

In order to assess inter- and intra-examiner reliability, the tests will be performed by two different operators and twice by the same operator, i.e. 3 identical examinations in total, in the first 20 patients included.

The duration of an examination will not exceed 15 minutes, i.e. a total duration of the ultrasound examination of 45 minutes for the first 20 patients (15 minutes for examination, 3 examinations).

The patient is in a sitting position and performs salivary swallowing attempts on request of the operator.

The convex probe will be placed under the chin, in the sagittal plane and between the edges of the hyoid bone and the mandible. The acoustic shadows of these bones will allow us to localise the structures and centre the image. (53)(54)

The following elements will be assessed:

- The position of the hyoid bone at rest and during swallowing;
- The thickness of the geniohyoid at rest and during swallowing;
- The contractility of the tongue ;
- The duration of contraction of the geniohyoid ;
- The number of swallowing attempts.

The linear probe will also be placed submentally, along a transverse axis, in order to qualitatively and quantitatively evaluate the suprahyoid muscles (55)

Qualitative analysis will be performed using the Heckmatt Score. (56) Quantitative analysis will be performed by measuring the thickness of the muscles at rest and during contraction. These two measurements will be used to calculate its thickening fraction. The thickness of the muscle is calculated by quantifying the distance between the upper and lower fascia of the muscle.

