9.7 Score validation

9.7.1 Reliability

With the correlation coefficient $\rho = 0.80$, a minimum value of the desired correlation coefficient $\rho_0 = 0.50$, a number of observations $k = 2$, $\alpha = 0.05$ and $\beta = 0.20$, the critical value for α from the normal distribution is 1.645 and the critical value for β from the normal distribution is 0.842. It is necessary to include 20 patients.

The study of inter and intra-examiner reproducibility will be evaluated with the Kappa coefficient. (64)

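### Read literally, Appendix 3 drops completed repeat ultrasound scans from the 20-patient reliability set when the later videofluoroscopy is not finalised, although the agreement analysis does not need that result

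*Combined protocol and SAP*

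**What the plan says.** All references are to the combined protocol and SAP.

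- **Size of the reliability set.** Section 9.7.1 (Reliability) ends its calculation with "It is necessary to include 20 patients".
- **Who is in it.** Section 7.2 has two operators scan, one of them twice, "i.e. 3 identical examinations in total, in the first 20 patients included".
- **Order of the day.** Section 8.3 puts ultrasound first, to keep its operator blind. Section 6.2.2 puts videofluoroscopy last.
- **Exclusion rule.** Appendix 3 (15.3) says of videofluoroscopy: "If the examination could not be finalised, the patient will be excluded from the protocol". It names altered vital parameters, discomfort or any other reason as grounds for stopping, and has the exclusion recorded in the observation booklet as due to a non-interpretable examination.
- **What is kept or allowed for.** Section 13.6 keeps data already collected when a patient withdraws consent, unless the patient asks otherwise. Section 12 mentions potential exclusions, but only in estimating recruitment capacity for the 100 patients. Neither section addresses the 20.

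**The concern.** A patient among the first 20 can complete all three scans and only afterwards have a videofluoroscopy that is not finalised. Appendix 3 then takes the patient out of the protocol as a whole, not just out of the comparison with videofluoroscopy.

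The reference result is needed to set thresholds (9.4), select and weight variables (9.5, 9.6) and estimate accuracy (9.7.2). It is not needed in 9.7.1, where ultrasound is compared with ultrasound. The rule therefore has no analytic purpose in the reliability analysis. It also leaves an odd contrast: a patient who withdraws consent has earlier data kept by default, while a consenting patient whose videofluoroscopy was stopped has no such provision.

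Reliability is part of every secondary objective in 2.2, and these 20 patients are the only source for it. Two things are at stake: precision in a set that is already small, and possibly who remains in it. If examinations stop mainly because patients tolerate them poorly, the remaining patients could be less frail than those the score is meant for.

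**Working it through.** **Inputs, all from 9.7.1:** expected coefficient ρ1 = 0.80; minimum coefficient ρ0 = 0.50; k = 2 observations per patient; α = 0.05; β = 0.20. The test is one-sided: "the critical value for α from the normal distribution is 1.645". The value for β is 0.842.

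**Step 1. The plan's own figure.** These inputs fit the Walter–Eliasziw–Donner formula for an intraclass correlation (ICC):

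n = 1 + 2k(zα + zβ)² / [(k − 1)(ln C0)²], where C0 = [1 + kρ0/(1 − ρ0)] / [1 + kρ1/(1 − ρ1)].

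- C0 = (1 + 2 × 0.50/0.50) / (1 + 2 × 0.80/0.20) = 3/9 = 1/3, so (ln C0)² = 1.207.
- (1.645 + 0.842)² = 6.185.
- n = 1 + 4 × 6.185/1.207 = 21.5, rounded up to 22.

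The stated 20 is close to this but slightly low.

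**Step 2. Power by number of patients analysed.** With the exact one-way ANOVA F distribution, power = P[F > (3/9) × F0.95], with n − 1 and n(k − 1) degrees of freedom. At n = 20, F0.95 = 2.137 and 2.137/3 = 0.712, which gives 76.8%.

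| Patients analysed | Power |
|---|---|
| 22 | 80.4% |
| 20 | 76.8% |
| 19 | 74.8% |
| 18 | 72.7% |
| 17 | 70.4% |
| 16 | 67.9% |

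Each patient lost from 20 costs about 2 to 2.5 points.

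**Step 3. Average effect of the exclusion.** The documents give no rate of unfinalised videofluoroscopy, so q is assumed, with independent losses. The chance of losing at least one patient is 1 − (1 − q)^20. Average power weights the exact power by the Binomial(20, 1 − q) number retained.

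| Assumed q | Chance of at least one loss | Average power | Cost of the exclusion (from 76.8%) |
|---|---|---|---|
| 1% | 18% | 76.4% | 0.4 points |
| 2% | 33% | 76.0% | 0.8 points |
| 5% | 64% | 74.7% | 2.1 points |
| 10% | 88% | 72.5% | 4.3 points |
| 20% | 99% | 67.6% | 9.2 points |

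**Step 4. Two shortfalls to keep apart.** With no exclusions at all, 80.0 − 76.8 = 3.2 points are already missing, because 20 is slightly too few. At q = 10% the total gap is 80.0 − 72.5 = 7.5 points, of which 4.3 come from the exclusion. At q = 5% the exclusion costs less (2.1) than the gap already there.

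**Step 5. The same loss as precision.** For an observed ICC of 0.80, the 95% interval is 0.57 to 0.92 with 20 patients and 0.55 to 0.92 with 18.

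**The case against.** The strongest reply is that the documents do not say that any scan is thrown away. Appendix 3 speaks of excluding the patient and recording the reason. It has no rule that completed ultrasound data are deleted or left out of the agreement analysis. Likewise, nothing forbids repeating the scans in the next patient until 20 are evaluable. This stands: the loss follows from the literal wording, and the absence of a replacement is silence, not a prohibition. But no other section keeps the data, and if the sponsor does intend to keep them, the same edit is needed to say so.

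Second, the power figures belong to an ICC test of 0.80 against 0.50, which appears only in the sizing sentence. Section 9.7.1 plans Kappa, and 9.2 plans Bland–Altman for quantitative and Kappa for qualitative agreement. This also stands. The figures illustrate scale and are not the power of the planned analysis, although losing complete sets of scans reduces precision under any of these statistics.

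Third, the effect may be small. Reliability is a secondary outcome, a rate of 1% or 2% costs less than one point, and the interval hardly moves when two patients are lost. This is fair, and it limits the weight of the point.

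A reader might go further and infer that reliability will be estimated in easier patients. The documents do not support that as a fact. Appendix 3 also allows any other reason for stopping, and a non-interpretable examination may be a technical failure. Nothing says that these patients are harder to scan.

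**Conclusion.** The point holds in a limited form. Appendix 3, followed as written, removes patients with complete repeat scans from a reliability set fixed at the first 20 included, for a reason that the agreement analysis does not need, and with no stated spare or replacement.

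The size depends on a failure rate that the documents do not give: under one point of power at 1% to 2%, about 2 points at 5%, about 4 at 10% and about 9 at 20%. This rests on the ICC sizing inputs, on independent losses, and on the literal reading of the exclusion. Selection against frailer patients is possible but not shown.

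A reader might infer that the exclusion rule is what takes the study below 80% power, or that power must fall. Neither follows. Power on the plan's inputs is already 76.8% with all 20 patients, and nothing more is lost unless at least one of them has an unfinalised videofluoroscopy. The change is worth making because it is nearly free, not because the damage is certain to be large.

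**What to change.** 1. **Appendix 3:** limit the exclusion to the analyses that need the videofluoroscopy result (9.4 to 9.6 and 9.7.2). This concerns analysis sets only and changes nothing about when or why an examination is stopped.
2. **Section 9.7.1:** state that all of the first 20 patients with completed repeat scans are analysed for inter- and intra-examiner agreement, whether or not videofluoroscopy was finalised.
3. **Patient-flow report:** show the two analysis sets separately, since they may differ by a few patients.

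The cost is two sentences of protocol wording and one addition to reporting. No extra patients, scans or staff are needed, because the scans are done before videofluoroscopy begins. Keeping the data is better than replacing the patients, since replacement would restore the number but not undo any selection.

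This leaves power at 76.8% on the plan's own inputs. Reaching 80% would take 22 evaluable patients and is a separate decision.
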